16. Active hepatitis (defined as (a) abnormal liver enzymes (Alanine aminotransferase (ALT), Gamma-glutamyl transferase (GGT), ALP > 3x Upper Limit of Normal (ULN) or (b)) for active hepatitis B or C infection, a positive Hepatitis B Virus (HBV) or Hepatitis C Virus (HCV) serology or patients with advanced chronic liver disease, confirmed by a Child-Pugh score of 10–15 (Class C).
17. Acute pancreatitis with no established source of infection.
18. Active hematological malignancy (previous hematological malignancies that are not actively treated are allowable).
19. Burns requiring ICU treatment.
20. Sepsis attributed to confirmed COVID-19.
21. Use of other investigational drugs within 5 half-lives of enrollment within 30 days (e.g., small molecules) / or until the expected pharmacodynamic effect has returned to baseline (e.g., biologics), whichever is longer; or longer if required by local regulations.
22. History of hypersensitivity to the study treatment or its excipients or to drugs of similar chemical classes.
23. Any medical conditions that could significantly increase risk of participants' safety by participating in this study according to investigator's judgement.
24. Women with a positive pregnancy test, pregnancy or breast feeding.
25. Women of child-bearing potential, defined as all women physiologically capable of becoming pregnant, unless they are using highly effective methods of contraception while taking study treatment and for 38 days of study treatment after stopping medication. Highly effective contraception methods include:
 - Total abstinence (when this is in line with the preferred and usual lifestyle of the participant. Periodic abstinence (e.g. calendar, ovulation, symptothermal, post-ovulation methods) and withdrawal are not acceptable methods of contraception
 - Female sterilization (have had surgical bilateral oophorectomy with or without hysterectomy), total hysterectomy, or bilateral tubal ligation at least six weeks before taking investigational drug. In case of oophorectomy alone, only when the reproductive status of the woman has been confirmed by follow-up hormone level assessment
 - Male sterilization (at least 6 months prior to screening). For female participants on the study, the vasectomized male partner should be the sole partner for that participant

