8.4 Safety and tolerability assessments

Safety assessments are specified below with [Section 1.3](#) Schedule of Activities detailing when each assessment is to be performed.

The following assessments will be considered safety measurements:

- Vital signs, including blood pressure, respiratory rate and body temperature at baseline Day 1 and at all post-baseline visits.
- Physical examination at screening, baseline Day 1, Day 14 and Day 90 visits.
- Local ECG at baseline Day 1 visit.

- Local arterial/venous blood gas sampling for PaO₂/carbon dioxide partial pressure (PaCO₂)/pH/HCO₃
- Local laboratory at screening, baseline Day 1 visit and at post-baseline visits.
 - Hematology at screening and baseline Day 1, Day 5, Day 14, Day 30 and Day 90 visits.
 - Clinical chemistry, including liver function parameters at screening and baseline Day 1, Day 5, Day 14, Day 30 and Day 90 visits.
 - Urinalysis at screening, baseline Day 1, Day 3, Day 5, Day 14, Day 30 and Day 90.
 - Coagulation parameters at screening, baseline Day 1, Day 5, Day 14, Day 30 and Day 90.
- Central laboratory for anti-drug antibodies at baseline (Day 1/ pre-dose) and at visits on Days 14, 30 and 90.
- Concomitant medication at screening and all visits from Day 1 to Day 90.
- AEs/SAEs during the duration of the study.
- Mortality (monitored continuously throughout the study)

For details on AE collection and reporting, refer to [Section 8.6](#).

As per [Section 4.5](#), during a public health emergency as declared by local or regional authorities i.e. pandemic, epidemic or natural disaster, that limits or prevents on-site study visits, regular phone or virtual calls can occur (every 4 weeks or more frequently if needed) for safety monitoring and discussion of the participant's health status until it is safe for the participant to visit the site again.

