8.4.4 Clinical safety laboratory tests

A local laboratory will be used for analysis of all specimens collected as part of routine clinical care and will be entered in the eCRF([Table 8-4](#)).

A central laboratory and sponsor designated laboratories will be used for analysis of the following: PK, immunogenicity, serum creatinine, cystatin C, serum purine metabolites, [REDACTED]

Details on the collection, shipment of samples and reporting of results by the central laboratory are provided to investigators in the laboratory manual.

Clinically notable laboratory findings are defined in [Section 10.3.1](#).

As per Section 4.5, during a public health emergency as declared by local or regional authorities' i.e. pandemic, epidemic or natural disaster, that limits or prevents on-site study visits, if participants cannot visit the site for protocol-specified safety lab assessments, an alternative lab (local) collection site may be used.

Local laboratory assessments may be performed on an as-needed basis to monitor safety tolerability to study drug (e.g. unscheduled visits).

Clinically significant abnormalities must be recorded as either medical history/current medical conditions or AEs as appropriate.

All abnormal lab results must be evaluated for criteria defining an AE and reported as such if the criteria are met. For those lab AEs, repeated evaluations are mandatory until normalization of the result(s) or until the result is no longer considered to be clinically significant.

In case of significant safety findings or a need to retest abnormal values, the local lab will be used to guide patient management. The results have to be made available to study investigators immediately, and the findings should be included in the eCRFs and the study database, properly identified as either local or central lab values.

In the case where a laboratory range is not specified by the protocol, but a value is outside the reference range for the laboratory at screening and/or initial baseline, a decision regarding whether the result is of clinical significance or not shall be made by the investigator (in consultation with the sponsor) and shall be based, in part, upon the nature and degree of the observed abnormality. The assessment may be repeated once prior to randomization.

Sample(s) will be collected at the time point(s) defined in the Assessment Schedule ([Table 1-2](#)).

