10.5 Appendix 5: Liver safety monitoring

To ensure participant safety and enhance reliability in determining the hepatotoxic potential of an investigational drug, a standardized process for identification, monitoring and evaluation of liver events has to be followed.

Please refer to [Table 10-2](#) in Appendix 5 for complete definitions of liver laboratory triggers.

Once a participant is exposed to study treatment, every liver event defined in [Table 10-2](#) should be followed-up by the investigator or designated personnel at the trial site, as summarized below. Additional details on actions required in case of liver events are outlined in [Table 10-3](#) and [Table 10-4](#). Repeat liver chemistry tests (i.e. ALT, AST, TBL, PT/INR, ALP and G-GT) to confirm elevation.

If a liver event is subsequently reported, any local liver chemistry tests previously conducted that are associated with this event should have results recorded on the appropriate eCRF.

If the initial elevation is confirmed, close observation of the participant will be initiated, including consideration of treatment interruption if deemed appropriate.

Hospitalization of the participant if appropriate.

Causality assessment of the liver event.

Thorough follow-up of the liver event should include:

These investigations can include based on investigator's discretion: serology tests, imaging and pathology assessments, hepatologist's consultancy; obtaining more detailed history of symptoms and prior or concurrent diseases, history of concomitant drug use, exclusion of underlying liver disease.

Obtaining a more detailed history of symptoms and prior or concurrent diseases.

Obtaining a history of concomitant drug use (including nonprescription medications and herbal and dietary supplement preparations), alcohol use, recreational drug use, and special diets.

Exclusion of underlying liver disease.

Imaging such as abdominal US, CT or Magnetic Resonance Imaging (MRI) , as appropriate.

Obtaining a history of exposure to environmental chemical agents.

Considering gastroenterology or hepatology consultations.

All follow-up information and procedures performed must be recorded as appropriate in the eCRF.

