10.5.1 Liver event and laboratory trigger definitions & follow-up requirements

Table 10-2 Liver event and laboratory trigger definitions

	Definition/ threshold
If ALT or AST normal at baseline:	
Liver laboratory triggers	$3 \times \text{ULN} < \text{ALT or AST} \leq 5 \times \text{ULN}$ $\text{TBL} > \text{ULN}^*$

Liver events	ALT or AST > 5 × ULN ALP > 2 × ULN (in the absence of known bone pathology) Total bilirubin > 3 × ULN (in the absence of known Gilbert syndrome) ALT or AST > 3 × ULN AND (TBL > 2 × ULN OR INR > 1.5) Potential Hy's Law cases (defined as ALT or AST > 3 × ULN and Total bilirubin > 2 × ULN [mainly conjugated fraction] without notable increase in ALP to > 2 × ULN) Any clinical event of jaundice (or equivalent term) ALT or AST > 3 × ULN accompanied by (general) malaise, fatigue, abdominal pain, nausea, or vomiting, or rash with eosinophilia Any adverse event potentially indicative of a liver toxicity
If ALT or AST elevated at baseline:	
Liver laboratory triggers	ALT or AST > 2 × baseline or > 200 U/L (whichever occurs first) TBL > ULN*
Liver events	ALT or AST > 3 × baseline or > 300 U/L (whichever occurs first) (ALT or AST > 2 × baseline or > 200 U/L [whichever occurs first]) AND (TBL > 2 × ULN OR INR > 1.5) ALT or AST > 5 × ULN ALP > 2 × ULN (in the absence of known bone pathology) Total bilirubin > 3 × ULN (in the absence of known Gilbert syndrome) Potential Hy's Law cases (defined as ALT or AST > 3 × ULN and Total bilirubin > 2 × ULN [mainly conjugated fraction] without notable increase in ALP to > 2 × ULN) Any clinical event of jaundice (or equivalent term) (ALT or AST > 2 × baseline or > 200 U/L [whichever occurs first]) accompanied by (general) malaise, fatigue, abdominal pain, nausea, or vomiting, or rash with eosinophilia Any adverse event potentially indicative of a liver toxicity

* Fractionate bilirubin, evaluate for cholestatic liver injury (ALP) or alternative causes of bilirubin elevation. Treat alternative causes according to local institutional guidelines

Table 10-3 Follow-up requirements for liver laboratory triggers - ALT, AST, TBL

ALT	TBL	Liver Symptoms	Action
ALT increase without bilirubin increase:			
If normal at baseline: ALT > 3 × ULN	Normal For participants with Gilbert's syndrome: No change in baseline TBL	None	
 Measure ALT, AST, ALP, GGT, TBIL, INR, albumin, CK, and Glutamate dehydrogenase (GLDH) in 48-72 hours. Follow-up for symptoms.

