If elevated at baseline: ALT > 2 × baseline or > 300 U/L (whichever occurs first)			
If normal at baseline: ALT > 5 × ULN for more than two weeks	Normal For participants with Gilbert's syndrome: No change in baseline TBL	None	
 Measure ALT, AST, ALP, GGT, TBIL, INR, albumin, CK, and GLDH in 48-72 hours. Follow-up for symptoms. Initiate close monitoring and workup for competing etiologies.
If elevated at baseline: ALT > 3 × baseline or > 300 U/L (whichever occurs first) for more than two weeks			
If normal at baseline: ALT > 8 × ULN	Normal	None	
ALT increase with bilirubin increase:			
If normal at baseline: ALT > 3 × ULN	TBL > 2 × ULN (or INR > 1.5) For participants with Gilbert's syndrome: Doubling of direct bilirubin	None	
If elevated at baseline: ALT > 2 × baseline or > 300 U/L (whichever occurs first)			
If normal at baseline: ALT > 3 × ULN	Normal or elevated	Severe fatigue, nausea, vomiting, right upper quadrant pain	
If elevated at baseline: ALT > 2 × baseline or > 300 U/L (whichever occurs first)			

Table 10-4 Follow-up requirements for liver laboratory triggers - Isolated Hyperbilirubinemia

Criteria	Actions required	Follow-up monitoring
Total Bilirubin (isolated)		
>1.5 – 3.0 ULN	
 Maintain treatment Repeat Liver Function Tests (LFTs) within 48-72 hours 	Monitor LFTs weekly until resolution to ≤ Grade 1 or to baseline
> 3 - 10 × ULN (in the absence of known Gilbert syndrome)	
 Interrupt treatment Repeat LFTs within 48-72 hours Hospitalize if clinically appropriate Establish causality Record the AE and contributing factors (e.g. conmeds, med hx, lab) in the appropriate eCRF 	Monitor LFTs weekly until resolution to ≤ Grade 1 or to baseline (ALT, AST, total bilirubin, Alb, PT/INR, ALP and GGT) Test for hemolysis (e.g. reticulocytes, haptoglobin, unconjugated [indirect] bilirubin)
> 10 × ULN	
 Discontinue the study treatment immediately Hospitalize the participant Establish causality Record the AE and contributing factors(e.g. conmeds, med hx, lab)in the appropriate eCRF 	ALT, AST, total bilirubin, Alb, PT/INR, ALP and GGT until resolution (frequency at investigator discretion)

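### For an elevated baseline, Table 10-3 pairs 2 × baseline with 300 U/L and names ALT only, while Table 10-2 uses 200 U/L for ALT or AST, so some liver triggers have no follow-up row

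*Protocol*

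**What the plan says.** Protocol Section 10.5.1 defines liver triggers and events in Table 10-2 and sets out follow-up for enzyme and bilirubin findings in Table 10-3.

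- **Table 10-2, elevated baseline.** The laboratory trigger is ALT or AST above 2 × baseline "or > 200 U/L (whichever occurs first"). The same 2 × / 200 U/L pair recurs in two liver events: one combined with raised TBL or INR, the other with symptoms. The 300 U/L limit appears only with 3 × baseline.
- **Table 10-3, elevated baseline.** The three corresponding rows (no bilirubin increase, bilirubin or INR increase, symptoms) set ALT above 2 × "baseline or > 300 U/L (whichever occurs first"). The table is titled "Follow-up requirements for liver laboratory triggers - ALT, AST, TBL", but no enzyme criterion in it names AST. AST appears only among the tests to be repeated.
- **Section 10.5, general text.** Follow-up is tied to liver events: "Once a participant is exposed to study treatment, every liver event defined in" Table 10-2. Its instruction to repeat the liver chemistry sets no deadline. The 48–72 hour limit is in Table 10-3 and, for isolated bilirubin, in Table 10-4.
- **Section 8.4.** The scheduled tests are "Clinical chemistry, including liver function parameters at screening and baseline Day 1, Day 5, Day 14, Day 30 and Day 90 visits".

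**The concern.** The two tables are meant to work together: one says who has triggered, the other says what to do. Table 10-3's next tier pairs 3 × baseline with 300 U/L, so with 300 U/L also in the lowest tier the absolute limit no longer separates the two (only the two-week duration does). That looks like a drafting slip, and Section 10.5 refers the reader to Table 10-2 for the full trigger definitions.

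A site applying Table 10-3 literally would not repeat the panel at 48–72 hours for some participants who met a Table 10-2 trigger. For a trigger that is not also a liver event, Table 10-3 is the only place that prescribes that repeat. Section 10.5 calls for a standardized process, and two adjacent tables with different limits and analytes cannot be applied uniformly across sites.

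**Working it through.** The plan has no figure to reproduce here. The check compares the two sets of limits.

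**1. The limits side by side (elevated baseline).**

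| Situation | Table 10-2 (ALT or AST) | Table 10-3 (ALT only) |
|---|---|---|
| Enzyme rise alone | > 2 × baseline or > 200 U/L | > 2 × baseline or > 300 U/L |
| With raised TBL or INR | > 2 × baseline or > 200 U/L | > 2 × baseline or > 300 U/L |
| With symptoms | > 2 × baseline or > 200 U/L | > 2 × baseline or > 300 U/L |
| Higher tier | > 3 × baseline or > 300 U/L | > 3 × baseline or > 300 U/L, for more than two weeks |

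The 2 × limb agrees; only the absolute limb differs.

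**2. Where the ALT gap lies.** Let b be baseline and x the on-study value. Trigger without a row means (x > 2b or x > 200) but not (x > 2b or x > 300). This reduces to 200 < x ≤ 300 with x ≤ 2b, and so requires b > 200/2 = 100 U/L.

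**3. When such a value also escapes the liver-event follow-up.** In both baseline groups Table 10-2 makes ALT or AST above 5 × ULN a liver event, so the value must satisfy x ≤ 5 × ULN and meet no other event criterion. With x > 200, this needs ULN > 200/5 = 40 U/L. The documents give no ULN, so a range of 30 to 60 U/L is assumed. Exclusion criterion 16 bars "abnormal liver enzymes (Alanine aminotransferase (ALT), Gamma-glutamyl transferase (GGT), ALP > 3x Upper Limit of Normal (ULN"); read as a cap of 3 × ULN on screening ALT, it gives:

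| Assumed ULN (U/L) | Exclusion cap, 3 × ULN | 5 × ULN | Trigger-only window, > 200 to min(300, 5 × ULN) |
|---|---|---|---|
| 30 | 90 | 150 | none |
| 40 | 120 | 200 | none |
| 45 | 135 | 225 | > 200 to 225 |
| 50 | 150 | 250 | > 200 to 250 |
| 60 | 180 | 300 | > 200 to 300 |

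The cap narrows the group but still allows a baseline above 100 U/L wherever the window is open.

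**4. Worked ALT example (ULN 50).** Baseline 120 is 2.4 × ULN, within the cap. On-study 220 is 220/120 = 1.83 × baseline and 220/50 = 4.4 × ULN. It meets the trigger (220 > 200), meets no Table 10-3 row (220 ≤ 240 and ≤ 300), and is not above 5 × ULN. At ULN 40 the same value is 220/40 = 5.5 × ULN, a liver event.

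**5. AST gap.** With a normal baseline, the trigger is above 3 and up to 5 × ULN. At an assumed ULN of 40 that is above 3 × 40 = 120 and up to 5 × 40 = 200 U/L. An isolated AST in this range has no Table 10-3 row. The same holds for AST-only triggers from an elevated baseline, at any ULN. Criterion 16 does not list AST, so baseline AST is not capped.

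**6. Wait for the next scheduled chemistry.** 14 − 5 = 9 days, 30 − 14 = 16 days, 90 − 30 = 60 days.

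**7. Check of the fix.** With 200 U/L in the 2 × rows of Table 10-3, the trigger and row conditions are identical. An enumeration of whole-number baseline and on-study pairs found none that triggered without a row.

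**The case against.** The text mismatch is not in dispute; the case against is about consequence.

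- **The ALT window may be empty.** At ULN 40 or below no case escapes both tables and Section 10.5, and above that several conditions must coincide. With about 15 participants on TIN816, possibly none will qualify. This stands, and it limits the size of the point.
- **The rows with bilirubin, INR or symptoms matter less.** These are liver events, so Section 10.5 already requires repeat chemistry, close observation and causality assessment. This largely stands, but Section 10.5 sets no time limit, so these cases still lose the 48–72 hour repeat.
- **AST is flagged elsewhere.** Table 10-1 makes an AST increase above 150% notable, and a rise from normal to above 3 × ULN is an increase of more than 200%. This stands for a normal baseline. The flag prompts a judgement of significance, however, not a timed repeat. It also misses a rise from an elevated baseline between 2 and 2.5 × (100% to 150% increase), and the ALT example above: (220 − 120)/120 = 83%.
- **Other routes to a repeat.** Section 8.4.4 says "For those lab AEs, repeated evaluations are mandatory until normalization of the result(s"), unscheduled tests are allowed, and inpatients have routine bloods. These help, but they depend on an AE judgement or local practice. The 9, 16 and 60 day intervals are therefore worst cases.
- **A sensible site would apply the rows to AST.** Probably so, given the title. That supports making the wording explicit.
- **No dosing decision depends on it.** Correct: treatment is a single infusion.

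**Conclusion.** The concern holds. Tables 10-2 and 10-3 conflict on the absolute limit in all three 2 × baseline criteria, and Table 10-3 omits AST from every enzyme criterion. The text establishes both without any assumption.

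The practical reach is small. For ALT it is confined to baselines above 100 U/L with values above 200 and up to 300 U/L, and the part outside liver-event follow-up depends on a ULN above 40 U/L, which the documents neither confirm nor exclude. The AST omission applies regardless of ULN and is partly mitigated by Table 10-1. What is at stake is the timing of a repeat liver panel. The primary PK analysis and the sample size are unaffected. This is a minor safety-monitoring correction that should be made.

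**What to change.** In Table 10-3, change 300 U/L to 200 U/L in the three rows that use 2 × baseline, to match Table 10-2, and keep 300 U/L with 3 × baseline. Replace ALT with ALT or AST in the table's enzyme criteria. Together these close both gaps. The cost is an edit to three limits and the analyte wording in one appendix table, plus a few more repeat liver panels.

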10.6 Appendix 6: Renal safety monitoring

Once a participant is exposed to study treatment, the following two categories of abnormal renal laboratory alert values should be assessed during the study period:

Serum creatinine increase $\geq 25\%$ compared to baseline during normal hydration status

Any one of the following:

Urine protein-creatinine ratio (PCR) $\geq 1\text{g/g}$ or $\geq 100\text{ mg/mmol}$, OR

New onset dipstick proteinuria $\geq 3+$, OR

New onset dipstick hematuria $\geq 3+$ (after excluding menstruation, Urinary tract infection (UTI), extreme exercise, or trauma)

Abnormal renal event findings must be confirmed within 24-48 hours after the first assessment.

Once a participant is exposed to study treatment, renal laboratory alerts or renal safety events should be monitored and followed-up by the Investigator or designated trial staff as summarized in [Table 10-5](#).

10.6.1 Specific Renal Alert Criteria and Actions and Event Follow-up

Table 10-5 Specific renal alert criteria and actions

Renal event	Actions
Confirmed serum creatinine increase of 25-49% from baseline	
 Consider causes and possible interventions Follow-up within 2-5 days
Confirmed serum creatinine increase $\geq 50\%$ from baseline (corresponds to KDIGO criterion for acute kidney injury)	
 Consider causes and possible interventions Repeat assessment within 24-48h if possible Consider patient hospitalization and specialized treatment
New onset dipstick proteinuria $\geq 3+$ OR Protein-creatinine ratio (PCR) $\geq 1\text{g/g Cr}$ (or mg/mmol equivalent as converted by the measuring laboratory)	
 Consider causes and possible interventions Assess serum albumin and serum total protein Repeat assessment to confirm
New onset of hematuria $\geq 3+$ on urine dipstick	
Assess and document
 
 Repeat assessment to confirm Exclude infection, trauma, bleeding from the distal urinary tract or bladder, menstruation Distinguish hemoglobinuria from hematuria Urine sediment microscopy Assess serum creatinine Consider bleeding disorder

10.6.1.1 Follow-up of renal events

Assess and document:

Urine dipstick and sediment microscopy evidence of drug-induced nephrotoxicity (DIN): crystals, red blood cells (dysmorphic/glomerular vs. non-dysmorphic/non-glomerular), white blood cells, tubular epithelial cells.

Blood pressure and body weight.

Serum creatinine, BUN, electrolytes (sodium, potassium, phosphate, calcium) and uric acid.

Urine output.

Review and record possible contributing factors to the renal event (co-medications, other co-morbid conditions) and any additional local diagnostic procedures performed in the CRF.

Monitor patient regularly (frequency at investigator's discretion) until:

Event resolution: serum creatinine within 10% of baseline or PCR < 1g/g creatinine, or albumin-creatinine ratio < 300 mg/g creatinine

Or

Event stabilization: serum creatinine level with $\pm 10\%$ variability over last 6 months or protein-creatinine ratio stabilization at a new level with $\pm 50\%$ variability over last 6 months.

Analysis of urine markers in samples collected over the course of the DIN event.

11 References

References are available upon request

Billings FT, Shaw AD (2014) Clinical trial endpoints in acute kidney injury. *Nephron Clin Pract*; 127(1-4):89-93.

Burnstock G, Verkhratsky A (2010) Long-term (trophic) purinergic signalling: purinoceptors control cell proliferation, differentiation and death. *Cell Death Dis*; (1):1.

CDER (2005) Estimating the Maximum Safe Starting Dose in Initial Clinical Trials for Therapeutics in Adult Healthy Volunteers. <https://www.fda.gov/media/72309/download>

